8.6. BLINDING

All subjects, Investigators and their staff (except unblinded pharmacist or designated site staff), and all Sponsor/CRO personnel involved in the management of the study will be blinded to treatment assignments.

The Information Technology department will be unblinded to treatment. As noted above, the Technology department is not otherwise involved with the study.

CONFIDENTIAL Page 79 of 108

Treatment unblinding for the study will occur after all clinical data have been received, data inconsistencies have been resolved, and the database is locked, except for safety reasons on a case-by-case basis (i.e., emergency unblinding).

The process for emergency unblinding will be outlined in details in the Randomization Plan. In addition, any subject that is unblinded for any reason will be identified and discussed in the final clinical study report.

8.7. TIME TO UNBLINDING

8.7.1. Interim Analysis

Unblinded treatment assignments for the interim analysis will only be given to an independent statistician who will conduct the analysis. For this analysis there will be no subject specific unblinding to any other personnel in the study.

8.7.2. Emergency Unblinding

Breaking the blind prematurely will be allowed only if the subject's well-being requires knowledge of the subject's treatment allocation. Every attempt will be made to maintain the blind throughout the study.

In the event of an urgent safety issue where the randomized treatment of a subject is necessary to manage and treat the affected study subject (e.g., unblinding subjects because of SAEs that meet "expedited criteria" and requires reporting to FDA and other global regulatory authority), the Investigator will contact the Medical Monitor. The Medical Monitor, in consultation with sponsor, will make a decision to unblind. If the decision has been made to unblind, a prompt written notification will be provided to the Investigator. The reason for unblinding must be recorded; however the investigator must not record the subject's treatment assignment in study documentation and must not reveal the subject's treatment assignment to the clinical monitor.

If reporting of an adverse event is to be performed unblinded as per regulatory authority guidelines, study-unrelated personnel will unblind the individual subject's treatment group and will perform the unblinded reporting. No treatment group information would be shared with study personnel.

8.7.3. Final Analysis

Treatment unblinding and release of the randomization codes of the investigational product assignments for the study will occur immediately following database lock when all randomized subjects have completed the study or discontinued from the study and after all clinical data have been received and data inconsistencies have been resolved.

8.8. INTERIM ANALYSIS

CONFIDENTIAL Page 80 of 108

An Interim Analysis (IA) will be conducted when approximately 50% (~195 subjects) of the study participants have been in the study for at least 4 weeks after randomization or are withdrawn from the study, whichever occurs first.

The main objectives of the IA are safety and sample size re-assessment.

The IA will have prospectively assigned rules and a method to protect the type I error rate and the integrity of the trial, due to the unblinded look. The IA will be conducted under the auspices of an independent Data Safety Monitoring Committee (DSMC) according to a written Charter. The procedures for this IA will be based on a standard operating procedure (SOP) that has a well-established a firewall to protect the integrity of the trial. The IA will be performed by an independent un-blinded statistician, who is not otherwise associated with the conduct of this trial.

The details of the interim analysis will be included in the Statistical Analysis Plan.

8.9. GENERAL STATISTICAL CONSIDERATIONS

All collected study data will be presented in subject data listings. Statistical analyses will be performed using SAS® for Windows, version 9.4 or later. Descriptive statistics (n, mean, standard deviation, median, minimum and maximum) will be presented for continuous variables. Frequencies and percentages will be presented for categorical variables.

8.9.1. Analysis Populations

8.9.1.1. Intent-to-Treat Population

The **Intent-to-Treat (ITT) population** is defined as all randomized subjects. This population will be used as the primary analysis population for analysis of the primary and secondary efficacy endpoints.

8.9.1.2. PP Population

The **Per Protocol (PP) population** is defined as the set of subjects who meet the ITT Population requirements and are not associated with any major protocol violations. This population will be identified before the database lock. This population will be used as the supportive analysis population for analysis of the primary and secondary efficacy endpoints.

8.9.1.3. Safety Population

The **Safety Population** will include all subjects who have received one dose of leronlimab (PRO 140) or placebo. This population will be used for the analysis of safety parameters or measurements.

8.9.2. Covariates

For efficacy analyses important prognostic factors that need adjustment will be specified in the Statistical Analysis Plan (SAP) for the study

CONFIDENTIAL Page 81 of 108

8.9.3. Missing Data

Every effort will be made to obtain required data at each scheduled evaluation from all subjects who have been randomized to minimize missing data. However, in the event when there is missing data the following imputation methods will be used.

For efficacy evaluations, multiple imputation methods will be used to handle missing data. This imputation method is a robust method to impute missing measurements. The imputation will be carried out in SAS version 9.4 or later using PROC MI. Each imputation model will include the stratification factor as a covariate in the model. The details of multiple imputation will be included in the statistical analysis plan.

8.10. ANALYSIS METHODS

A Statistical Analysis Plan (SAP) will be developed and approved before the database is locked. The SAP will present the detailed statistical methodology to be used in analyzing the data from this trial.

8.10.1. Subject Disposition

The disposition of all subjects who signed an ICF will be provided. The number of subjects screened, screen failed, randomized, received at least one treatment, completed, and discontinued during the study, as well as the reasons for all discontinuations will be summarized by treatment group. Disposition and reason for study discontinuation will also be provided as a by-subject listing.

8.10.2. Demographic and Baseline Characteristics

Demographics and baseline characteristics including medical history, will be summarized by treatment group using appropriate descriptive statistics.

8.10.3. Concomitant Medications/Therapies

Concomitant medications/therapies will be summarized separately for the Safety population. All prior and concomitant medications recorded in the case report form will be coded to matching Anatomic Therapeutic Classification codes using the most recent version of the WHO Drug Dictionary. Descriptive summaries by treatment group will be prepared using the coded term. All concomitant medications/therapies recorded in the case report form will be listed.

8.10.4. Efficacy Analyses

Primary Analysis

The ITT population will be the primary population for the analysis of the efficacy endpoints of the study.

Primary Endpoint

CONFIDENTIAL Page 82 of 108

The primary endpoint for this study is the proportion of subjects with Mortality at Day 28 between leronlimab and placebo. The difference in the Day 28 mortality between the leronlimab and placebo treatment groups will be compared using Logistic regression model.

Secondary Endpoints

To maintain the trial-wise Type I error rate at 0.05, a closed test procedure will be used for the secondary endpoints. The order of the secondary endpoints will prospectively specified in the SAP.

Analysis of the secondary and exploratory endpoints will be summarized according to the variable type:

- Continuous data summaries will include:
 - o If the Normality assumption is met, Analysis of Covariance (ANCOVA) would be used.
 - If the Normality assumption is not met, a non-parametric method or a rank ANCOVA analysis i.e., an ANCOVA analysis on rank-transformed data will be used.
- Categorical data summaries will be based on Logit model will be used.
- Time-dependent data: Cox proportional hazards model will be used to analyze time dependent data and to depict the time to event data.

8.10.5. Supportive Analysis

To assess the consistency of the Primary Analysis results, supportive analysis will be conducted using the Intent to Treat (ITT) and Per Protocol (PP) populations. Statistical methodology for the supportive analyses will be the same as that of the primary analysis, with the exception of the analysis population used.

8.10.6. Subgroup Analysis

Subgroup analyses will be conducted for the predefined stratification factors (Section 8.5) for the study. Additional exploratory subgroup analysis will be conducted using the baseline clinical characteristics and laboratory parameters such as, CD4/CD8 ratio and IL-6. The details will be prospectively specified in the SAP.

Safety Summaries

8.10.6.1. Adverse Events

Adverse events will be coded using the most recent version of Medical Dictionary for Regulatory Activities (MedDRA). Treatment Emergent AE's (TEAE) are defined as events with an onset on or after the first treatment. TEAEs will be summarized by System Organ Class and preferred term by treatment group. The following TEAE summaries will be provided:

• Overall (i.e., regardless of severity or relationship to treatment);

CONFIDENTIAL Page 83 of 108

• By intensity (mild, moderate, severe, life threatening or death);

- By causality (definitely, probably, possibly, remotely or unrelated);
- By impact on study treatment (dose increased, dose not changed, dose rate reduced, dose reduced, drug interrupted, drug withdrawn, not applicable, or unknown).

In addition, separate summaries of serious adverse events, and adverse events resulting in discontinuation of study treatment will be presented.

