The **Intent-to-Treat (ITT) population** is defined as all randomized subjects. This population will be used as the primary analysis population for analysis of the primary and secondary efficacy endpoints.

The **Per Protocol (PP) population** is defined as the set of subjects who meet the ITT Population requirements and are not associated with any major protocol violations. This population will be identified before the database lock. This population will be used as the supportive analysis population for analysis of the primary and secondary efficacy endpoints.

The **Safety Population** will include all subjects who have received one dose of leronlimab (PRO 140) or placebo. This population will be used for the analysis of safety parameters or measurements.

Analysis Methods

Efficacy Analyses:

Primary Endpoint: Mortality rate at Day 28

The proportion of subjects with mortality at Day 28 will be compared between the leronlimab and placebo treatment groups using Logistic regression model.

Secondary Endpoints: To maintain the trial-wise Type I error rate at 0.05, a closed test procedure will be used for the secondary endpoints. The order of the endpoints will be specified in the Statistical Analysis Plan (SAP).

Analysis of the secondary endpoints will be summarized according to the variable type and will be detailed in the SAP:

Continuous data:

CONFIDENTIAL Page 13 of 108

Name of Sponsor/Company:					
CytoDyn, Inc.					
Name of Study Product:	Name of Study Product:				
Leronlimab (PRO 140)					
Protocol Number: Indication:					
CD12_COVID-19	Coronavirus Disease 2019 (COVID-19)				

- If the Normality assumption is met, Analysis of Covariance (ANCOVA) would be used.
- If the Normality assumption is not met, a non-parametric method or a rank –ANCOVA
 analysis i.e., an ANCOVA analysis on rank-transformed data will be used.
- Categorical data summaries will be based on Logit model will be used.
- Time-dependent data: Cox proportional hazards model will be used to analyze time dependent data and Kaplan-Meier methods will be used to depict the time to event data.

Safety Assessments

The Safety population will be used for the analysis of safety outcomes.

For continuous variables, data will be summarized by treatment using n, mean, SD, minimum and maximum values. For categorical variables, data will be summarized by treatment using frequency and percentage. No inferential statistics are planned.

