8.3. SAMPLE SIZE DETERMINATION AND RATIONALE

This is a randomized study with two treatment groups. The subjects will be randomized to the treatment groups (leronlimab or placebo) in a 2:1 ratio.

A total of three hundred ninty (390) subjects will be randomized in a 2:1 ratio to leronlimab or placebo groups with the goal of having 369 subjects (246 subjects in the leronlimab and 123 in the placebo group) complete the study.

The sample size is obtained based on the assumption that there will be a clinically meaningful difference in the rate of Day 28 mortality (i.e., 15% which is 45% Day 28 mortality rate for the placebo group versus 30% Day 28 mortality rate in the leronlimab group). This sample size is based on using a 2-sided Z-tset test with 80% power and an overall significance level of 0.05. The expected dropout rate is 5%. To accommodate subject attritions due to the potential discontinuations, it is recommended randomizing an estimated 390 subjects (260 in the leronlimab group and 130 placebo group). Sample size is estimated using PASS sample size software, tests for two proportions.

CONFIDENTIAL Page 78 of 108

A single arm, non-randomized, open-label phase is added to the protocol after completion of enrollment in the Randomized Phase of the study in order to provide access to leronlimab for the eligible patients. Approximately, 100 subjects are expected to be enrolled in the non-randomized phase. Enrollment will remain open until the decision is made by Sponsor and/or FDA to close the recruitment. No statistical power calculation is used for the sample size calculation for the non-randomized portion of the trial.

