9.2. REPORTING OF ADVERSE EVENTS

Report initiation for all AEs and SAEs will begin at the time of the first treatment visit and continue until the end of final study visit. All events will be followed to resolution or until the subject completes the study. A final assessment of outcome will be made at that time.

All AEs must be recorded in the subject's medical records and on the CRF. AEs will be reported using customary medical terminology along with the following information: the onset and end dates, whether the event is considered to be a SAE (see Section 9.3), the impact the event had on study treatment (see Section 9.2.1), the Common Terminology Criteria for Adverse Events (CTCAE) grade (intensity) of the event (see Section 9.2.2), the causality of the event (see Section 9.2.3), whether treatment was given as a result of the event (see Section 9.2.4), and the outcome of the event (see Section 9.2.5)

[figure not shown]

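### Adverse event percentages are taken over follow-up that ends at death, so the design's own mortality difference pushes overall SAE incidence one way and non-fatal AE incidence the other.

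*Protocol*

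**What the plan says.** Protocol 8.10.6.1 and SAP 9.3.1 both state that "TEAEs will be summarized by System Organ Class and preferred term by treatment group". They add tables by intensity (with death as one category), causality and impact on treatment, plus separate SAE and discontinuation summaries. The form of the tables is set in the Protocol Synopsis, Safety Assessments: "For categorical variables, data will be summarized by treatment using frequency and percentage". SAP 9.1 likewise specifies counts and percentages. The Synopsis plans no inferential statistics for safety.

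Under Protocol 9.2, AE and SAE reporting "will begin at the time of the first treatment visit and continue until the end of final study visit". That final visit is V7, nominally Day 42 (Protocol Table 4-2). Protocol 9.3 makes any AE that results in death an SAE.

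Protocol 8.3 sizes the trial on "45% Day 28 mortality rate for the placebo group versus 30% Day 28 mortality rate in the leronlimab group".

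SAP 9.1.5 lists and summarises drug administration only. Neither document plans a time-at-risk denominator, an event rate or a cumulative incidence function for AEs. SAP 8.7.4 does recognise that death cuts observation short, but only for length of stay and duration of ventilation.

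**The concern.** A subject who dies on Day 10 contributes 10 days in which a non-fatal AE could be recorded; a survivor contributes about 42. If the drug works as the design assumes, the leronlimab arm has more time in which to accumulate non-fatal AEs, and a crude percentage makes no allowance for it. If the drug raised mortality, a real excess of non-fatal AEs would be partly hidden.

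Overall SAE incidence has the opposite problem. Each death enters as an SAE, so the percentage of subjects with any SAE largely repeats the primary endpoint and says little about non-fatal harm.

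Safety is named alongside efficacy in the study objective (Protocol section 2). It will be judged by reading these tables across arms, and the DSMC receives AEs, SAEs and deaths on the same basis (SAP 5.1.5). From n (%) alone a reader cannot tell which of the two effects is at work.

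**Working it through.** **Inputs from the documents.** Day 28 mortality is 45% and 30%, and the test is a "2-sided Z-tset test with 80% power and an overall significance level of 0.05" with subjects "randomized in a 2:1 ratio to leronlimab or placebo groups" (Protocol 8.3). AE collection runs to nominal Day 42.

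**The plan's own figure.** With an unpooled Z-test, n(placebo) = (1.960 + 0.842)² × (0.45×0.55 + 0.30×0.70/2) / 0.15² = 122.97. That gives 123 + 246 = 369, as stated. 369/0.95 = 388.4, consistent with 390 randomised. The sample size reproduces and is not at issue.

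**Assumptions the documents do not give.** The base case has a constant death hazard h = −ln(1 − m)/28, which is 0.02135/day on placebo and 0.01274/day on leronlimab. The non-fatal AE hazard a is identical in both arms. Every death is recorded as a fatal SAE.

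**Time at risk to Day 42.** With no deaths after Day 28, mean time is m/h + 14(1 − m).
- Placebo: 0.45/0.02135 + 14×0.55 = 28.8 days.
- Leronlimab: 0.30/0.01274 + 14×0.70 = 33.4 days. The ratio is 1.16.
- If the death hazard continues to Day 42: 27.7 and 32.5 days, ratio 1.17.
- If the mean day of death is varied from 7 to 21, time is 42(1 − m) + m × (mean day), and the ratio runs from 1.20 to 1.10.

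**Non-fatal AEs, constant hazard, no deaths after Day 28.** Crude incidence = a/(a+h) × (1 − e^(−28(a+h))) + e^(−28(a+h)) × (1 − e^(−14a)).

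| a per day | Placebo | Leronlimab | Ratio |
|---|---|---|---|
| 0.005 | 13.1% | 15.1% | 1.15 |
| 0.01 | 24.1% | 27.6% | 1.15 |
| 0.02 | 40.8% | 46.4% | 1.14 |

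If the death hazard continues to Day 42, the ratios for these hazards are 1.17, 1.16 and 1.15. For an AE affecting 80% of placebo subjects, the leronlimab figure is 86.4%, ratio 1.08. If events can occur only in the first 14 or 7 days, the ratio is 1.06 or 1.03.

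**Any SAE with deaths counted, death hazard continuing to Day 42.** Incidence = 1 − e^(−42(a+h)).

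| Non-fatal SAE hazard per day | Placebo | Leronlimab | Ratio |
|---|---|---|---|
| 0.0005 | 60.1% | 42.7% | 0.71 |
| 0.002 | 62.5% | 46.2% | 0.74 |
| 0.01 | 73.2% | 61.5% | 0.84 |
| 0.05 | 95.0% | 92.8% | 0.98 |

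With no deaths after Day 28, incidence is 1 − (1 − m)e^(−42a) and the four ratios are 0.68, 0.72, 0.85 and 0.98. Total AE events per subject, with one fatal event per death, can go either way: ratio 0.85 at 0.01 non-fatal AEs/day and 1.09 at 0.10.

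**Would a rate cure it?** The first-event rate is first events divided by days to first event, death or Day 42. At a constant equal hazard its ratio is 1.00. With early events it is not. These runs again use identical AE hazards in both arms and no deaths after Day 28.

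| AE hazard | Crude ratio | Unsplit rate ratio |
|---|---|---|
| 0.01/day on Days 0-14, then none | 1.06 (11.3% vs 12.0%) | 0.92 (0.439 vs 0.402 per 100 days) |
| 0.01/day on Days 0-7, then none | 1.03 | 0.89 |
| 0.01/day on Days 0-14, then one-tenth | 1.08 | 0.93 |

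Splitting the rate at Day 14 restores equality in the first and third rows, where the hazard is constant within each period. In the second row the Day 0-14 rates are 0.546 and 0.531 per 100 days, ratio 0.97.

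**The case against.** The strongest reply is that the crude percentage is not an error. All treated subjects share one planned window, and expected dropout is only 5%. So n/N estimates the probability of having the event with death as a competing event, which is a legitimate quantity. This stands, and it is why the percentages should stay.

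A reader might infer that arms should be compared on the rate instead. The calculations do not support that. Dosing is on Days 0 and 7, so clustering of events early in follow-up is plausible. In that case an unsplit rate makes the better-surviving arm look falsely safer, and in two of the three cases above it errs by more than the percentage does.

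It can also be said that the plan already handles part of this. Intensity tables have a death category, fatal outcome is recorded once per subject (Protocol 9.2.5), and mortality is reported at Days 14, 28 and 42. That helps, but the overall, SAE and SOC/preferred-term tables still mix fatal and non-fatal events, and none shows time at risk.

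Finally, no safety test is planned and no stopping rule uses these percentages. That limits the consequence to how descriptive tables are read.

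**Conclusion.** The point holds as a reporting weakness with two opposite artefacts. Under the design mortality and identical non-fatal hazards, overall SAE incidence is lower in the arm with fewer deaths, ratio about 0.71 to 0.98 depending on the assumed non-fatal hazard. Non-fatal AE percentages are higher in that arm: about 14 to 15% with a constant hazard to Day 42, about 8% for an AE affecting 80% of placebo subjects, and 3 to 6% if events fall in the first 7 to 14 days.

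It is tempting to conclude that the arm with fewer deaths will show about 15% more AEs and SAEs generally. The documents do not support that. Protocol 9.3 counts deaths as SAEs, which reverses the direction for overall SAE incidence. The 15% applies only to non-fatal events of low to moderate frequency with a steady hazard. AE hazards and death timing are not given, so all these figures are illustrative. The sample size and the primary analysis are unaffected.

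**What to change.** In Protocol 8.10.6.1 and SAP 9.3.1, for the overall TEAE, SAE and SOC/preferred-term tables:

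- Tabulate non-fatal and fatal events separately by arm.
- For non-fatal events, show beside n (%) the total subject-days at risk and the number of subjects with a first event per 100 subject-days. Time at risk runs from first dose to first event, death, last contact or V7, whichever is earliest.
- Preferably give the rate in two periods, Days 0-14 and after Day 14.
- Keep the crude percentages. State that they estimate the probability of the event with death as a competing event, and that the rate is not the sole scale for comparing arms.

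The cost is added rows and columns derived from first-dose, AE-onset, death and last-contact dates, all already collected. The downside is that the rate assumes a roughly constant hazard within each period, so some distortion remains where events cluster within the first days.
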